8.4.7. Regulatory Aspects of Adverse Event Reporting

The Sponsor is responsible for submitting reports of SAEs associated with the use of the study interventions to the appropriate Regulatory Authority (e.g., the US FDA), Investigators, and IRB/IEC/Central Ethics Committee in accordance with all applicable regulations and guidelines.

It is the responsibility of the Investigator to notify the IRB of SAEs that occur at his or her site per IRB requirements. Investigators will be notified of all suspected, unexpected serious adverse reactions (SUSARs; 7-/15-Day Safety Reports) that occur during any clinical studies that are using duvelisib. Each site is responsible for notifying their IRB/IEC/Central Ethics Committee of these additional SUSARs in accordance with local regulations.

8.4.8. Overdose

For this study, overdose is defined as a daily dose of a study intervention higher than the prescribed daily dose.

In the case of overdose, clinic staff should be notified immediately, and supportive care is to be given if needed and as indicated. Subjects should be informed to contact their doctor immediately if they have taken an overdose and should stop taking study interventions.

Overdoses will not be considered SAEs unless the outcome of the overdose meets seriousness criteria as defined in Section 8.4.2. In the event of an overdose that causes an SAE, the Sponsor should be notified within 24 hours. The subject should be carefully monitored for potential adverse reactions and symptomatic treatment instituted as per institutional SOC. The Investigator will determine if and when dosing should resume.

8.4.9. Pregnancy

Any pregnancy must be reported to the Sponsor or designee within 24 hours of the Investigator's knowledge of the pregnancy using a Pregnancy Report Form.

Pregnancy per se is not considered an AE unless there is cause to believe that the study interventions may have interfered with the effectiveness of a contraceptive medication or if the outcome of the pregnancy meets SAE criteria (miscarriage or congenital anomaly/birth defect, etc.), in which case it should be reported in the same manner and timelines as an SAE. In addition, any infant death or congenital anomaly occurring after 30 days that the Investigator suspects is related to the in-utero exposure to the study interventions should also be reported as an SAE. Hospitalization for normal delivery of a healthy newborn is not an SAE.

Since duvelisib and pembrolizumab have not been evaluated in pregnant or nursing women, the treatment of pregnant women or WCBP who are not using highly effective contraception is contraindicated (see Table 23 and Section 10.4 for instructions on pregnancy testing and contraception).

Pregnancies occurring in subjects or partners of male subjects during the study intervention period and until 30 days after the subject's last dose of study interventions are considered immediately reportable events. If a pregnancy occurs in a subject, study interventions must be discontinued immediately. The pregnant woman should be referred to an obstetrician/gynecologist experienced in reproductive toxicity for further evaluation and counseling. The Investigator will observe the pregnant woman until completion of the pregnancy and must notify the Sponsor of the outcome within 24 hours of the Investigator's knowledge of the pregnancy outcome using a Pregnancy Outcome Form. This notification includes pregnancies resulting in live, "normal" births.

8.5. Pharmacokinetics

PK samples will be collected during the study.

- Blood samples will be collected to evaluate the PK of duvelisib and metabolite IPI-656 at the visits and time points defined in the SoA (Table 2 and Table 4)

- On the days when postdose PK samples are collected, specific timing for the administration of duvelisib and pembrolizumab is required (see [Table 2](#) and [Table 4](#)), as follows:
 - Stage 1: On C1D8, duvelisib will be administered at the start of the visit after the predose PK, pharmacodynamic, and blood sample collection. Blood samples to evaluate the PK of duvelisib and metabolite IPI-656 will be collected at 1 and 2 hours after duvelisib administration. Pembrolizumab will not be administered until the biopsy for biomarkers has been collected; the optimal timing for collection of the biopsy is approximately 2 to 4 hours after duvelisib administration, however, a tumor biopsy at a later time during this clinic visit on C1D8 is acceptable. The fourth PK sample should be collected at approximately 2 to 4 hours after duvelisib dose, as soon as possible after the biopsy, and prior to pembrolizumab administration.
 - Stage 1: On C2D1, duvelisib will be administered 30 minutes before the start of the pembrolizumab infusion.
 - Stage 2: On C1D1, duvelisib will be administered at the start of the visit after the predose PK and blood sample collection. Pembrolizumab will be administered 30 minutes after the collection of the 2-hour postdose duvelisib PK sample.
- Predose samples are preferred, therefore on the days that include PK assessments the morning dose of duvelisib should be administered in the clinic to facilitate collection of samples before dosing. However, the sample should still be collected even if the morning dose of duvelisib has already been taken. The date and time of the sample collection and date and time of the previous duvelisib dose must be recorded for all collected samples.
- Additional PK samples beyond those listed in the SoA ([Table 2](#) and [Table 4](#)) may be requested (when feasible) for any unusual safety event. (i.e., an AE different in type and severity from that which is expected in the setting of duvelisib use).
- Specific instructions on sample collection and handling will be provided in a separate Laboratory Manual.
- Retained duplicate PK samples may also be used to evaluate safety or efficacy aspects related to concerns arising during or after the study.
- Genetic analyses will not be performed on these PK samples.
- Subject confidentiality will be maintained.

8.6. Pharmacodynamics

Pharmacodynamic biomarkers are described in Section [8.8](#).

8.7. Genetics

Normal germline genetic studies are not evaluated in this study. Tumor genomic studies may be conducted as part of exploratory biomarker research (Section [8.8](#)). A swab of non-tumor tissue (genomics control) will be collected to compare polymorphisms in the subject's non-tumor cells vs the tumor cells.

8.8. Biomarkers

Blood and tissue specimens are to be collected according to the SoA ([Table 2](#) and [Table 4](#)) and assessments will be conducted to evaluate potential biomarkers. Each of the specimens listed may be analyzed at a central laboratory or at a specialized laboratory vendor as determined by the Sponsor, for the various biomarkers outlined below:

1. Pharmacodynamic markers of target inhibition in HNSCC
2. Immunophenotypes and functional tests of major immune populations in the blood and/or feces
3. Cytokines and other circulating biomarkers
4. Prognostic markers assessed by DNA, RNA, and protein analysis from tissue and blood specimens

In addition, C-reactive protein levels in blood (a clinical safety laboratory assessment) will be evaluated as a potential biomarker ([Table 23](#)).

Sample collections may be reduced, or limited to certain sites/countries, based on emerging data or feasibility. Reductions/limitations may be implemented before amendment of the protocol. Specific collection and processing details (e.g., serum or plasma) will be described in the Laboratory Manual. Any increase in the number or type of samples collected will require a protocol amendment.

8.8.1. Tumor Biopsy and Colon Biopsy

In Stage 1 of the study, 2 tumor biopsies (Screening/C1D1 and C1D8) are mandatory, as specified in the SoA (see [Table 2](#)). The 2 biopsies do not need to be done on the same lesion.

- Screening/C1D1 biopsy: Archival tissue beyond the 30-day Screening window and up to 6 months before C1D1 may be considered in place of the required Screening/C1D1 biopsy after consultation with the Sponsor, as long as no intervening systemic regimen had been taken during that time frame.
- C1D8 biopsy: The optimal timing for collection is approximately 2 to 4 hours after duvelisib administration but before pembrolizumab administration. However, a tumor biopsy at a later time during this clinic visit on C1D8 is acceptable.

In Stage 2, an optional tumor biopsy may be collected after the first cycle (on C2D1) for an exploratory analysis of biomarkers ([Table 4](#)). If collection of the biopsy is not feasible on C2D1, a biopsy collected after the second cycle (on C3D1) would also be acceptable.

Collection procedures and amounts are described in the Laboratory Manual.

If available, aliquots of any colon biopsies taken due to colitis or Grade ≥ 3 diarrhea or as SOC for any immune-mediated AEs should also be provided.

8.9. Medical Resource Utilization and Health Economics

Health economics/medical resource utilization and health economics parameters are not evaluated in this study.

9. STATISTICAL METHODOLOGY

A detailed description of the statistical methodology for this study can be found in the Statistical Analysis Plan (SAP). Deviations from the statistical analyses outlined in this protocol will be indicated in the SAP; any further modifications will be noted in the final CSR.

9.1. Statistical Hypotheses

This study will test the null hypothesis that the ORR is $\leq 16\%$ against the alternative that ORR is $\geq 44\%$. The ORR (proportion of subjects achieving CR or PR) according to RECIST v 1.1 ([Eisenhauer 2009](#)) will be estimated on the modified Intent-to-Treat (mITT) population (i.e., all subjects who receive at least 1 dose of duvelisib in combination with at least 1 dose of pembrolizumab). For this study "response" is defined as a confirmed response, per RECIST v 1.1 ([Eisenhauer 2009](#)), unless otherwise specified. Details for determination of confirmation of response will be provided in the SAP. A 2-sided exact 95% CI will be calculated.

The ORR of 16% being used for the null hypothesis is based on multiple sources. The pembrolizumab prescribing information ([Keytruda 2019](#)) reports an ORR for pembrolizumab monotherapy of 16% in subjects previously treated with a platinum-containing therapy in the KEYNOTE-012 study. An ORR of 16% is also reported for subjects naïve to anti-PD-L1 therapy in the KEYNOTE-055 study ([Bauml 2017](#)). Further, the ORR for pembrolizumab monotherapy is reported in the USPI as 19%. Therefore, an uninteresting response rate of 16% will be used for all subjects in this study.

The evaluation of the primary endpoint will be conducted at the highest dose that is tolerated during the DLT evaluation. Therefore, if the initial dose of 25 mg BID is not tolerated but the reduced dose of 15 mg BID is tolerated, the primary endpoint will be evaluated in all subjects starting at the tolerated dose.

9.2. Sample Size Determination

The study will follow a Simon two-stage design ([Simon 1989](#)). In the first stage, approximately 13 subjects will be accrued. If there are 2 or fewer responses (CR or PR) in these 13 subjects, further accrual in the study may be stopped. However, all available data will be considered before termination.

In Stage 2, 17 additional subjects will be accrued for a total of 30 subjects in the final analysis. The null hypothesis will be rejected if 10 or more responses (CR or PR) are observed in 30 subjects. This design yields an overall type I error rate of 5% and power of 90% when the true response rate is 44%.

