2.4.3. Overall Benefit/Risk Conclusion

As early phase clinical studies are designed to provide information about the safety and efficacy of an investigational drug, subjects enrolled in the study cannot expect to receive a direct benefit from an experimental treatment.

Although pembrolizumab is approved for the treatment of patients with HNSCC, the ORR (19% for first-line treatment in patients with CPS ≥ 1 and 16% for second-line treatment) was relatively low ([Keytruda 2019](#)). Based on the strong antitumor synergy (i.e., inhibition of tumor growth and prolonged survival) for duvelisib in combination with a PD-1 inhibitor observed in the nonclinical in vivo studies and the manageable AE profile for duvelisib in patients with hematologic malignancies, subjects with R/M HNSCC could potentially benefit from improved response rates.

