9.4.1. General Considerations

Hypothesis testing will be used for the interim (Stage 1) and final (Stage 1 + Stage 2) analyses of the efficacy endpoint of ORR. No formal hypothesis testing will be used for any other endpoints or other study data, such as demographics and safety data.

Tabulations will be produced for appropriate disposition, demographic, baseline, efficacy, and safety parameters. For categorical variables, summary tabulations of the number and percentage of subjects within each category (with a category for missing data) of the parameter will be presented, as well as 2-sided 95% CIs, unless stated otherwise. For continuous variables, the number of subjects, mean, median, standard deviation, minimum, and maximum values will be presented. Time-to-event data will be summarized using Kaplan-Meier (KM) methodology using 25th, 50th (median), and 75th percentiles with associated 2-sided 95% CIs, as well as number and percentage of censored observations.

The Investigator's assessments of disease response will be used as the basis for the evaluation of the primary and secondary efficacy endpoints.

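### The stated 5% type I error does not belong to the stated design: at the 16% null, rejecting at 10 of 30 has an exact one-sided error of 1.4%

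*Combined protocol and SAP*

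**What the plan says.** Section 9.1 and the Synopsis set the null at an ORR of at most 16% and the alternative at 44% or more. Section 9.1 gives its sources for the null: 16% from two pembrolizumab studies, and then "Further, the ORR for pembrolizumab monotherapy is reported in the USPI as 19"%. It concludes: "Therefore, an uninteresting response rate of 16% will be used for all subjects in this study". Section 2.4.3 identifies the higher figure as "19% for first-line treatment in patients with CPS" of at least 1, and gives 16% for second-line treatment. Both groups are eligible under inclusion criterion 3.

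Section 9.2 specifies about 13 subjects in Stage 1 and 17 more in Stage 2. Accrual may stop at 2 or fewer responses in Stage 1, and the null is rejected at 10 or more responses in 30. The stop is discretionary: "However, all available data will be considered before termination". The section then states: "This design yields an overall type I error rate of 5% and power of 90% when the true response rate is 44"%. The Synopsis repeats this.

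The Simon criterion (optimal or minimax) and the sidedness of the 5% are not given. Only the interval is described: "A 2-sided exact 95% CI will be calculated". Section 9.4.1 confines formal testing to ORR: "No formal hypothesis testing will be used for any other endpoints or other study data".

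**The concern.** A null rate, an alternative rate and a set of two-stage boundaries fix the type I error and the power exactly. The plan gives all of these inputs, so its 5% and 90% can be checked directly. A maximum of 30 subjects with a cut-off of 10 looked too demanding for a one-sided 5% test of 16% against 44%.

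If the 5% is wrong, the protocol misreports an operating characteristic of its only formal test, and the SAP may inherit the figure. The two candidate null rates would also give different readings of a result at the boundary. Which rate the boundary was built on should therefore be settled before response data are seen.

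**Working it through.** **Inputs** (Sections 9.1 and 9.2): p0 = 0.16; p1 = 0.44; n1 = 13; continue if X1 ≥ 3; n2 = 17; reject if X1 + X2 ≥ 10.

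**Formula, futility stop applied:** P(reject | p) = Σ over x = 3 to 13 of P[Bin(13, p) = x] × P[Bin(17, p) ≥ 10 − x].

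**Power first, at p = 0.44:** 0.9004. This matches the stated 90%, so the rule is being read as the sponsor read it.

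**Type I error at p = 0.16, by Stage 1 count:**

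| x | P(X1 = x) | P(X2 ≥ 10 − x) | Product |
|---|---|---|---|
| 3 | 0.20489 | 0.01179 | 0.00242 |
| 4 | 0.09757 | 0.04230 | 0.00413 |
| 5 | 0.03345 | 0.12237 | 0.00409 |
| 6 | 0.00850 | 0.28406 | 0.00241 |
| 7 | 0.00162 | 0.52660 | 0.00085 |
| 8 or more | | | 0.00021 |

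The sum is 0.0141, or 1.41%, against the stated 5%.

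**Other readings of the rule at p = 0.16:**

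- Futility stop never applied, P[Bin(30, 0.16) ≥ 10]: 1.50% (power 91.48%).
- Stage 2 opened at 2 or more Stage 1 responses, as Section 4.1 allows: 1.49%.
- 5% read as two-sided, so 2.5% in the upper tail: the attained tail is still 1.41%.
- Rejection at 9 or more instead: 3.61% (4.03% non-binding).

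None gives 5%.

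**Null rate at which the stated rule has 5% error:** 19.5% with the stop applied, 19.3% without it.

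**Exhaustive search for Simon designs with p1 = 0.44 and power of at least 90%** (written r1/n1, r/n; reject if responses exceed r):

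| p0 | One-sided error limit | Minimax design | Attained error |
|---|---|---|---|
| 0.16 | 5% | 1/10, 6/22 | 4.78% |
| 0.16 | 2.5% | 2/14, 8/27 | 2.00% |
| 0.17 | 2.5% | 2/13, 9/30 | 2.11% |
| 0.18 | 5% | 2/14, 8/27 | 4.01% |
| 0.19 | 5% | 2/13, 9/30 | 4.25% |
| 0.20 | 5% | 4/25, 10/32 | 4.11% |

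The optimal design for 16% at 5% is 2/11, 7/27 (error 4.34%), which is not the protocol's either. The protocol's boundaries appear for 19% at 5% (4.51% if the stop is not applied) and for 17% at 2.5%. Of those two nulls, only 19% is cited in Section 9.1, and only the 19% match uses the stated 5%.

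**Agreement with the planned interval.** Exact (Clopper-Pearson) two-sided 95% lower limits for n = 30 are 14.7% at 9 responses, 17.3% at 10 and 19.9% at 11. Ten is therefore the smallest count whose planned interval excludes 16%, but that interval does not exclude 19%. The one-sided 95% lower limit at 10/30 is 19.3%.

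**The case against.** The strongest reply has four parts.

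- **5% as a ceiling.** In a Simon design the type I error is usually a limit, and 1.4% respects it. The mismatch is conservative, power is right, and no patient or decision is affected. All of that stands, and it limits the consequence. But the sentence says what the design yields, and a design chosen for 16% against 44% at 5% and 90% would not need 30 subjects: the minimax maximum is 22.
- **A two-sided 5% test of 16%.** With 13 + 17 subjects fixed and 2.5% in the upper tail, 9 of 30 fails (3.61%) and 10 of 30 passes (1.41%). The cut-off also agrees with the planned two-sided 95% interval. This is a coherent explanation of the cut-off and cannot be excluded, since the documents name no Simon criterion. It does not make the attained error 5%, and the hypotheses are written one-sided.
- **The 19% match is not unique.** Correct: 17% at 2.5% gives the same boundaries. A 19% origin is an inference, and the error in the stated figure does not depend on it.
- **The null is explicit.** Section 9.1 does adopt 16%. What is unclear is only which null the boundary was derived from.

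A further fair point is that Stage 1 is described as approximately 13. With the same cut-offs, 12 of 29 gives 1.07% error and 86.8% power at 44%; 14 of 31 gives 1.82% and 92.6%. Corrected figures should name the exact sizes.

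**Conclusion.** The concern holds. For exactly 13 and 30 subjects and the stated cut-offs, the one-sided type I error at 16% is 1.41% (1.50% with the futility stop ignored). The stated 5% is about 3.5 times that (5 / 1.41). The stated power of 90% is correct.

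The calculation assumes independent responses with a common rate and uses no input from outside the protocol. It shows a misreported operating characteristic, not a loss of error control: rejection at 10 of 30 is valid against 16%, and the bar is stricter than a one-sided 5% test of 16% needs. That the design was built for 19% is plausible but not established by the documents.

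**What to change.** Keep the patient numbers and the boundaries. Before the Stage 1 ORR data are analysed, make one of two corrections in Sections 9.1 and 9.2 and the Synopsis. Carry it into the SAP, because Section 9 says "Deviations from the statistical analyses outlined in this protocol will be indicated in the SAP".

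**(a) Keep the null at 16%.** Replace the sentence with: *With exactly 13 and 30 subjects, the one-sided type I error is 1.4% at an ORR of 16% (1.5% if the futility stop is not applied), and power is 90.0% at an ORR of 44%.* This is the smallest repair, leaves the stated hypothesis alone and agrees with the planned 95% interval. It costs one sentence in two places, and the plan then openly describes a test stricter than 5%.

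**(b) Only if 19% was the intended null.** State the null as an ORR of at most 19%, with one-sided type I error 4.2% (4.5% non-binding) and power 90.0%. Also report the one-sided 95% lower limit (equivalently a two-sided 90% interval), because at exactly 10 of 30 the planned two-sided 95% interval starts at 17.3% and still contains 19%. This changes the stated primary hypothesis to a slightly harder one and adds one confidence limit.

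Which null suits the mixed first-line and later-line population is the sponsor's judgement; Section 9.1 currently chooses 16%. Under either option, state that the test is one-sided and name the Simon criterion used.

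Do not lower the cut-off to 9 of 30 to use up the 5%. It would reject 16% while the planned interval (lower limit 14.7%) includes it, and the error would be 9.1% if the true pembrolizumab-alone rate were 19%.

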9.3. Populations for Analyses

The populations for the analyses are described in [Table 16](#).

Table 16: Populations for Analyses

Population	Description
Enrolled ^a	All subjects who sign the ICF
DLT Evaluable	The first 6 subjects in Stage 1 who complete Cycle 1 and who receive $\geq 75\%$ of the scheduled duvelisib doses during Cycle 1 or who have a DLT during Cycle 1
ITT	All subjects who receive at least 1 dose of duvelisib. The ITT analysis set will serve as the primary analysis set for all safety endpoints and baseline parameters.
mITT	All subjects who receive at least 1 dose of duvelisib in combination with at least 1 dose of pembrolizumab. The mITT analysis set will serve as the primary analysis set for all efficacy endpoints.

Abbreviations: DLT: dose-limiting toxicity; ICF: informed consent form; ITT: intent-to-treat; mITT: modified intent-to-treat.

^a “Enrolled” means a subject's, or their legally acceptable representative's, agreement to participate in a clinical study after completion of the informed consent process. Potential subjects who are pre-screened for the purpose of determining eligibility for the study but do not sign an ICF are not considered enrolled.

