4. STUDY DESIGN

4.1. Overall Design

This is a multicenter, non-randomized, open-label, Phase 1b/2 study of duvelisib in combination with pembrolizumab in subjects with R/M HNSCC who are eligible for pembrolizumab monotherapy based on the current pembrolizumab prescribing information ([Keytruda 2019](#)). This study will be conducted at multiple sites in the US and will include approximately 13 subjects in Stage 1 and 17 additional subjects in Stage 2, for a total of 30 subjects in the final analysis.

The study will follow a Simon two-stage design ([Simon 1989](#)).

The study stages are depicted in [Figure 1](#) and the treatment/imaging schemes for Stage 1 and Stage 2 are depicted in [Figure 2](#) and [Figure 3](#), respectively.

Subjects will receive duvelisib 25 mg BID orally (PO) in combination with pembrolizumab 200 mg every 3 weeks (q3w) intravenously (IV).

In **Stage 1**, subjects will have a 1-week lead-in with duvelisib before the initiation of combination therapy with duvelisib and pembrolizumab. Approximately 13 subjects are planned to be accrued in this stage. The first 6 subjects will be assessed for dose-limiting toxicities (DLTs). The DLT evaluation period will be Cycle 1 (4 weeks or 28 days): the 1-week duvelisib monotherapy lead-in period followed by 1 dose of pembrolizumab in combination with 3 additional weeks of continuous dosing of duvelisib. Every effort will be made to administer the first dose of pembrolizumab on Day 8 of Cycle 1 (C1D8). If the first dose of pembrolizumab on C1D8 is delayed, every effort should be made to delay the subsequent dosing of the next cycle (within the protocol-allowed window of 3 days) to achieve as close to a 3-week interval between pembrolizumab doses as possible. The Medical Monitor needs to be consulted for such adjustments to ensure uniformity of approach and to account for subject-specific circumstances. For example, if the third day of the C2D1 window falls on a weekend, an additional adjustment would need to be made on a case-by-case basis. In the event of a delay of the start of pembrolizumab therapy, DLTs will be evaluated at the end of the third week of combination therapy.

The DLT evaluation period will be used to assess DLTs in the first 6 subjects.

- If there is ≤ 1 DLT in the 6 DLT-evaluable subjects, additional subjects will be enrolled to bring the total dosed in Stage 1 to approximately 13 subjects.

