5.6. Replacement of Subjects

During the DLT evaluation period in Stage 1, subjects who discontinue duvelisib before the end of Cycle 1, for reasons other than a DLT, or who receive < 75% of the scheduled duvelisib doses during Cycle 1 may be replaced.

Any other subjects who withdraw from the study for reasons other than PD or treatment-related toxicity before receiving at least 1 cycle of study intervention may be replaced.

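### The primary ORR set leaves out Stage 1 subjects who take duvelisib but stop before their first pembrolizumab dose, so ORR can only move up relative to all treated subjects, probably by little.

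*Combined protocol and SAP*

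**What the plan says.** - **Analysis set.** Section 9.1 estimates ORR, with a two-sided exact 95% interval, on the mITT population: at least one dose of duvelisib in combination with at least one dose of pembrolizumab. Table 16 in Section 9.3 adds: "The mITT analysis set will serve as the primary analysis set for all efficacy endpoints". The ITT set in the same table (at least one dose of duvelisib) is primary for safety and baseline data only.
- **Lead-in.** Section 4.1 gives Stage 1 subjects one week of duvelisib alone. Pembrolizumab is due on Day 8 of Cycle 1, and Table 1 shows a window of ±5 days for that visit. In Stage 2 both drugs start on Cycle 1 Day 1.
- **Decision rules.** Section 9.2: "If there are 2 or fewer responses (CR or PR) in these 13 subjects, further accrual in the study may be stopped". Then: "In Stage 2, 17 additional subjects will be accrued for a total of 30 subjects in the final analysis". And: "The null hypothesis will be rejected if 10 or more responses (CR or PR) are observed in 30 subjects".
- **Who is counted.** For Stage 1, Section 4.1 counts dosed subjects: "additional subjects will be enrolled to bring the total dosed in Stage 1 to approximately 13 subjects". For the 30, Section 9.2 refers only to subjects in the final analysis.
- **Replacement.** The first sentence of Section 5.6 allows replacement, during the DLT evaluation period, of subjects who discontinue duvelisib before the end of Cycle 1 for reasons other than a DLT. The second covers any other subjects who withdraw "for reasons other than PD or treatment-related toxicity before receiving at least 1 cycle of study intervention may be replaced".

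**The concern.** Membership of the primary set depends on something that happens after treatment starts. The protocol foresees subjects who would fail this condition. Table 12 has a part for the duvelisib lead-in only, and some of its outcomes are discontinuation of duvelisib. Section 6.6.2 says that discontinuing duvelisib also ends pembrolizumab. Section 6.7.2 says that a subject with a DLT should in general stop the study interventions. Death, clinical deterioration or withdrawal in that week has the same effect.

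These subjects have received study treatment and have not responded. In a single-arm trial judged against a fixed 16%, removing them can only favour the treatment. The filter acts essentially in Stage 1 alone, and the text describes no ORR analysis on the ITT set. A second question is whether the rule (10 of 30) and the interval (on mITT) share a denominator.

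**Working it through.** **Inputs.** Null rate 16% (Section 9.1: "Therefore, an uninteresting response rate of 16% will be used for all subjects in this study"); alternative 44%; continue if more than 2 of 13 respond; reject at 10 or more of 30 (Section 9.2). The number d of Stage 1 subjects who never receive pembrolizumab is not in the documents. I assume d = 1 to 3, all non-responders.

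**The plan's own figures.** P(reject) = Σ over x₁ = 3 to 13 of Bin(x₁; 13, p) × P(Bin(17, p) ≥ 10 − x₁). At p = 0.44 this is 90.04%, which reproduces the stated 90% power. At p = 0.16 it is 1.41%, inside the stated 5%.

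**Shift in the estimate.** With x responses among 30 dosed subjects, mITT ORR = x/(30 − d), which is the all-dosed ORR times 30/(30 − d). For x = 10, with exact (Clopper-Pearson) 95% limits:

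| d | ORR | 95% CI | Relative increase |
|---|---|---|---|
| 0 | 10/30 = 33.3% | 17.3 to 52.8 | none |
| 1 | 10/29 = 34.5% | 17.9 to 54.3 | 3.4% |
| 2 | 10/28 = 35.7% | 18.6 to 55.9 | 7.1% |
| 3 | 10/27 = 37.0% | 19.4 to 57.6 | 11.1% |

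**Agreement of interval and rule, if the 30 are dosed subjects.** Nine responses fail the rule whatever d is.

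| d | ORR | 95% CI | Excludes 16%? |
|---|---|---|---|
| 0 | 9/30 = 30.0% | 14.7 to 49.4 | no |
| 1 | 9/29 = 31.0% | 15.3 to 50.8 | no |
| 2 | 9/28 = 32.1% | 15.9 to 52.4 | no |
| 3 | 9/27 = 33.3% | 16.5 to 54.0 | yes |

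So disagreement with 9 responses needs at least 3 losses. With 8 responses it needs at least 7 (8/24 has lower limit 15.6%, 8/23 has 16.4%).

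**How likely is that disagreement?** Assume that each of the 13 is lost independently with probability 2%, 5% or 10%, that none is replaced, that true ORR in the remaining subjects is 30%, and that the trial continues only with more than 2 Stage 1 responses. The probability of a conflict is then about 0.02%, 0.3% and 1.5%.

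**Effect on false positives.**
- *Losses not replaced:* Stage 1 has 13 − d mITT subjects, and the cutoffs do not move. At p = 0.16 in mITT, P(reject) falls from 1.41% to 1.07%, 0.79% and 0.57% for d = 1, 2, 3.
- *Losses replaced, so that mITT stays at 13 + 17:* if the all-dosed rate is 16%, the Stage 1 mITT rate is 0.16 × (13 + d)/13. P(reject) is then 1.8%, 2.2% and 2.7%, still below 5%.

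**The case against.** **The mITT set fits the objective.** Table 5 asks about the combination, and the 16% comes from pembrolizumab-treated subjects. How the external studies defined their denominators is not visible here, so the bias against 16% itself cannot be measured. This stands. It does not remove the shift relative to the trial's own treated subjects, because the lead-in is part of the Stage 1 regimen.

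**The mechanism is narrow.** The first scheduled on-treatment scan is at 10 weeks in Stage 1, so routine imaging will not show progression in the lead-in. Lead-in toxicity is often handled without stopping duvelisib, and a subject whose pembrolizumab is only delayed stays in mITT. This also stands and is why the effect is probably small.

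**The SAP may deal with it.** Sections 9 and 9.4 leave detail to an SAP that is not in the supplied text, so an ITT analysis of ORR there cannot be ruled out.

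Four stronger readings are tempting but not supported:
- *The rule is written for 30 dosed subjects, so test and estimate conflict.* Only the Stage 1 count is explicitly of dosed subjects. If the 30 are mITT subjects, the two agree.
- *Subjects lost to progression or toxicity are never replaced.* The first sentence of Section 5.6 allows replacement of any non-DLT discontinuation in the DLT period. Non-replacement therefore applies to DLTs, and outside that period to progression or treatment-related toxicity. Replaced subjects still leave mITT.
- *The mITT set costs power.* The rule counts responses, and lost subjects are non-responders in either set, so changing the set recovers none.
- *The test becomes too liberal.* Removing non-responders adds no responses. Without replacement the fixed rule only gets stricter.

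**Conclusion.** The point holds as one about estimation and clarity. Subjects treated in the Stage 1 lead-in can leave the primary ORR after dosing, and each such loss moves the estimate and interval upwards relative to all treated subjects. At 10 responses the shift is about 1.1 percentage points for one loss (34.5 − 33.3, before rounding) and 3.7 for three, against an interval about 35 points wide. The loss counts are assumptions.

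The denominator of the final rule is ambiguous. A conflict between interval and rule is possible only if the 30 are dosed subjects, and it is improbable at the loss rates tried. The change is worth making because it is cheap, but it is not critical to the design.

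**What to change.** In Sections 9.1 and 9.2 and Table 16, make the existing ITT set (at least one dose of duvelisib, restricted to subjects starting at the tolerated dose) the denominator for the primary ORR, its exact interval and the 13 and 30 subject rules. Count subjects without a response assessment as non-responders. Report ORR on mITT as a supporting analysis. State whether a replaced subject still counts towards the 13 and the 30, because keeping both the lost and the replacement subject takes the ITT set above 30.

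With 30 dosed subjects, interval and rule then agree on both sides of the cutoff: 10/30 has lower limit 17.3% and rejects, 9/30 has 14.7% and does not. Power and type I error remain as designed (90.0% and 1.4%).

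The cost is a wording change in the protocol and SAP, and a reported ORR that may be slightly lower. No new data are needed.
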